Randomization by blocks will be used, with stratification for type of surgery (robotic/laparoscopic vs. open) and subcohort membership (agrees to 30 day ultrasound/does not agree to 30 day ultrasound). Currently at Johns Hopkins approximately 40% of RPs are performed open, with the remainder robotic or laparoscopic, and the subcohort is planned to include 200 patients. Note that patients are randomized within each of the 4 subgroups formed by cross classification of these 2 strata, not randomized to the strata. Therefore, anticipated sizes of the 4 strata are

1. open RP/subcohort member, n=80
2. open RP/not subcohort member, n=186
3. robotic RP/subcohort member, n=120
4. robotic RP/not subcohort member, n=280

Because the above numbers are subject to variability in the choice of surgical approach, randomization lists will increase the number in each of the surgical categories by 20%, i.e. 320 and 480 random assignments will be generated for open and robotic surgeries, respectively. An undisclosed block size will be used to prevent any ability to predict next treatment assignment. The randomization lists will be generated by [name] using SAS PROC PLAN. Although this uses a pseudorandom number generator it has the advantage of reproducibility when the same seed is used. [name] will maintain the randomization list, password protected, on a remote drive maintained by the Department of Urology, and will provide the random assignment to the study coordinator as each patient is enrolled. Because surgery dates are scheduled weeks in advance, there is no concern about inability to access the randomization list. A biostatistician who works for [name] and is not otherwise connected to this trial will also have access to the random assignments and can provide them to the study coordinator in the unlikely event that [name] is unavailable. Only [name] and the biostatistician ([name]) have access to the remote drive.

b. Primary outcome variable.

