Two planned interim analyses of the primary endpoint will be conducted, after one-third and two-thirds of patients have undergone RP. Early stopping for efficacy or futility will be assessed at these time points. Details are provided below under Interim Analyses.

Statistical analyses: The treatment and control groups will be compared to identify any imbalance after randomization in relevant characteristics. Comparisons will include factors such as age, race, BMI, comorbidities, prostate volume, tumor stage, operative time, and blood loss. Discrete factors will be compared with chi-squared test, and continuous factors will be compared with t-test or Wilcoxon ranksum test if data do not conform to a Gaussian distribution. Analysis of the primary outcome (symptomatic VTE) will compare 30 day post-RP rates between the treatment and control groups, using chi-squared test. Logistic regression will be used if adjustment is required for any potential confounders not balanced by randomization, with the treatment effect estimated by the odds ratio and 95% confidence interval. Similar comparison of univariate rates, and adjusted odds ratios will be used for the 3 primary safety endpoints (lymphocele, hematoma, occurrence of major bleeding), and for the secondary outcome of any VTE (restricted to patients who undergo the 30 day lower extremity Duplex ultrasound). Secondary endpoints with a continuous metric (blood loss, surgical drain output, number of imaging tests (surveillance bias)) will be compared in univariate fashion using t-test or Wilcoxon ranksum, and adjusted analyses will use linear regression. Note that analysis of drain output is confined to patients with drains placed, so it is not protected by the randomization, potentially limiting interpretability if the number of patients is small and confounding factors are not well balanced. All analyses of primary and secondary outcomes will be based on intention to treat (ITT). Per protocol analyses will also be conducted, but treatment success will be based on ITT.

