Additional subanalyses (both ITT and per protocol) will be performed with stratification by arm compliance (proportion of scheduled subcutaneous heparin doses administered), performance of pelvic lymphadenectomy (including number of nodes removed), performance of open or robotic surgery (including differences in operative time), and other demographic and comorbidity criteria (including history of VTE, cancer, and other risk factors included in the Caprini Score) to identify patients at highest risk for VTE. Surveillance bias will also be evaluated, as mentioned above, by the differential performance of diagnostic imaging.

e. Interim Analyses.

Two interim analyses of the primary endpoint are planned with potential early stopping for efficacy or futility. O'Brien-Fleming boundaries were used, as implemented in PASS v. 11 (NCSS Software, Inc., Kaysville, UT). The total sample size needed for 82% power with a 1-sided test is 666 (333 per treatment arm), based on 2000 simulations. The interim analyses will be conducted after 1/3 and 2/3 of patients are enrolled (222 and 444, respectively). Alpha-spending at the 2 interim analyses and final analysis is .001,

.015, and .033 (cumulative alpha spent .001, .015, .048), respectively. The futility boundaries at the 1st and 2nd interim analyses, and final analysis are $p=0.816$, 0.272 , and 0.070 , respectively.

At each interim analysis the rates of the 3 safety endpoints (lymphocele, major bleeding, and hematoma) will also be evaluated and 95% confidence intervals calculated. Unacceptable rates for these endpoints are $\geq 15\%$, $\geq 5\%$, and $\geq 10\%$, respectively. If lower 95% confidence bounds meet or exceed these unacceptable rates the trial will be halted for further review and consideration of early stopping.

8. Risks

- a. Medical risks, listing all procedures, their major and minor risks and expected frequency.

Administration of subcutaneous heparin:

1. Major risks:

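### The main test of blood loss, drain output and imaging count ignores the factors on which randomisation is stratified; it is conservative, and loses power, to the extent that blood loss differs by surgical approach

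*Combined protocol and SAP*

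**What the plan says.** Section 7d (Statistical analyses) states that the continuous secondary endpoints, namely blood loss, drain output and number of imaging tests, "will be compared in univariate fashion using t-test or Wilcoxon ranksum, and adjusted analyses will use linear regression". It names no covariates, no outcome scale and no stratified test.

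Section 7a describes block randomisation "with stratification for type of surgery (robotic/laparoscopic vs. open) and subcohort membership", giving four strata. It adds that "approximately 40% of RPs are performed open, with the remainder robotic or laparoscopic".

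Three other statements in section 7 bear on the point:

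- For the baseline comparisons, a list that includes blood loss, "continuous factors will be compared with t-test or Wilcoxon ranksum test if data do not conform to a Gaussian distribution".
- The only trigger given for adjustment is stated for the binary outcomes: "Logistic regression will be used if adjustment is required for any potential confounders not balanced by randomization".
- The additional subanalyses include stratification by "performance of open or robotic surgery (including differences in operative time"). Their stated purpose is to identify the patients at highest risk of VTE.

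On drain output, section 7d itself warns that "analysis of drain output is confined to patients with drains placed, so it is not protected by the randomization".

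**The concern.** Blocking within surgical approach balances the arms on approach. The analysis has to use approach as well if it is to benefit from that. An unstratified test leaves the open-versus-robotic difference in its error variance, although the design has already removed that difference from the treatment contrast. The treatment estimate is not biased, but the test rejects too rarely.

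Nothing else in the plan clearly repairs this. The adjustment trigger is imbalance after randomisation, and a factor balanced by design would not set it off. The open/robotic subanalysis is aimed at VTE risk and is not the overall treatment comparison of blood loss.

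Whether heparin increases blood loss is aim 6 in section 2, and section 4c blinds the urologist to the preoperative dose in order to protect that measurement. On a harm question a conservative test errs in the unsafe direction, because a real increase is more easily reported as no difference.

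**Working it through.** **The plan's own figure.** The only stated power is 82% for symptomatic VTE (5% v 1.5%, 333 per arm, one-sided 0.05). The fixed-sample formula is Φ[(p₁ − p₂ − 1.645·SE₀)/SE₁]. Here SE₀ = √(2 × 0.0325 × 0.9675/333) = 0.01374 and SE₁ = √((0.0475 + 0.014775)/333) = 0.01368. This gives Φ[(0.035 − 0.0226)/0.01368] = 81.8%, so the figure reproduces. It does not bear on blood loss, for which the documents give no SD, target effect, alpha or power.

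**Inputs from the documents.** N = 666, with 333 per arm. From the strata in section 7a, open = 80 + 186 = 266 and robotic = 120 + 280 = 400. The open share is π = 266/666 = 0.399, so π(1 − π) = 0.240.

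**Assumed inputs.** Blood loss is lognormal with log-scale SD s = 0.6 within each approach. The ratio R of open to robotic medians runs from 1 to 3. Heparin raises blood loss by 15% throughout. Tests are two-sided at 5%.

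**Mechanism, on the log scale.** With balance by design, the treatment contrast has true standard error s√(4/N) = 0.6 × √(4/666) = 0.0465. The effect is ln 1.15 = 0.1398, so effect/SE = 3.006. A test that ignores approach uses the larger SD, σ = √[s² + π(1 − π)(ln R)²], instead of s. Hence:

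- power = Φ(3.006 − 1.96·σ/s)
- actual size = 2[1 − Φ(1.96·σ/s)]

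| R | σ | σ/s | Actual size | Power ignoring approach | Power with approach |
|---|---|---|---|---|---|
| 1 | 0.600 | 1.000 | 5.0% | 85.2% | 85.2% |
| 1.5 | 0.632 | 1.053 | 3.9% | 82.7% | 85.2% |
| 2 | 0.689 | 1.149 | 2.4% | 77.5% | 85.2% |
| 3 | 0.806 | 1.343 | 0.8% | 64.5% | 85.2% |

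**Simulation of the planned Wilcoxon test, same assumptions.** Unstratified against stratified Wilcoxon power is 83% v 83% at R = 1, 74% v 84% at R = 2 and 61% v 84% at R = 3. At R = 1.5 the loss is about 3 points. With no heparin effect and R = 3, the unstratified tests reject 0.9% to 1.2% of the time against a nominal 5%. The stratified Wilcoxon rejects 5.3%, and regressions with approach 5.1% to 5.3%.

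**Sensitivity to the assumed SD.** Here the effect was reset for each SD so that log regression with approach has about 80% power (1,500 runs per cell). Entries are unstratified v stratified Wilcoxon power.

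| R | s = 0.5 | s = 0.6 | s = 0.8 |
|---|---|---|---|
| 1 | 78.1 v 78.1% | 78.2 v 78.4% | 78.3 v 78.5% |
| 1.5 | 73.0 v 78.2% | 75.5 v 79.2% | 77.4 v 78.6% |
| 2 | 65.5 v 79.0% | 70.5 v 79.7% | 72.7 v 77.5% |
| 3 | 43.1 v 79.7% | 48.2 v 76.8% | 63.4 v 78.8% |

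The direction holds in every cell with R above 1. The loss at R = 3 runs from 15 to 37 points.

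**Choice of scale.** Both regressions below include approach, and only the form of the heparin effect is varied (s = 0.6):

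| Assumed effect | Raw scale | Log scale |
|---|---|---|
| 15% increase in all patients, medians 600/200 mL | 67% | 86% |
| 50 mL increase in all patients, medians 600/200 mL | 52% | 99% |
| 25% increase in open cases only, medians 600/200 mL | 72% | 47% |
| 8% of heparin patients lose an extra 800 mL, medians 400/200 mL | 85% | 61% |

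Neither scale is better throughout.

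No calculation was made for drain output or imaging counts, because the documents give neither a distribution nor the number of patients with drains.

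**The case against.** A reader might infer that the plan gives up much of its power. The documents do not support that without condition. They give no blood-loss distribution and no open/robotic difference, and a large loss needs an assumed ratio of about two or more. At ratios near 1 the Wilcoxon test loses almost nothing.

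A reader might also infer that the plan mishandles skewed data by using raw-scale regression. The text says only linear regression; it names no scale and rules out neither a log outcome nor approach as a covariate. The Wilcoxon test already copes with skewness, so its loss comes from ignoring approach.

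A third tempting step is to require a log-scale model. A lognormal simulation with a constant percentage effect favours that model by construction. The last two rows of the scale comparison show that a log analysis can lose power when harm is concentrated in open cases or in a few heavy bleeds.

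Finally, these are secondary endpoints with no power target and no stopping role, and bleeding harm is judged mainly by the three primary safety outcomes. All of this stands and limits the weight of the point. It does not remove the mismatch between a stratified randomisation and an unstratified main test.

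**Conclusion.** The concern holds in a limited form. The main comparison of blood loss, drain output and imaging count ignores the randomisation strata, and nothing in the plan commits any treatment comparison of them to include those strata. For blood loss, the cost under assumed lognormal data (log-scale SD 0.6, 15% increase) is about 0, 3, 10 and 23 points of Wilcoxon power at open/robotic ratios of 1, 1.5, 2 and 3. At three-fold the test's actual size is about 1%. These sizes rest wholly on the assumed distribution; the direction does not, provided that blood loss differs by approach. The effect on drain output and imaging counts is not quantified. The primary VTE conclusion is unaffected.

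**What to change.** Amend section 7d, before the data are unblinded, as follows:

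- Make the main treatment comparison of blood loss, drain output and imaging count carry the randomisation strata. Use either linear regression on treatment, surgical approach and subcohort, or a stratified (van Elteren) Wilcoxon test, and say which. Keep the unstratified test as a sensitivity check.
- State that the strata are included whether or not any imbalance is seen.
- Fix the outcome scale in advance, with a reason tied to the expected form of the heparin effect, and report the other scale as a sensitivity analysis.
- Keep the existing caution on drain output. Adjusting for the strata does not restore the protection of randomisation in patients selected for having a drain.

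The cost is wording only: approach and subcohort are already recorded for randomisation, and no further patients or data are needed. If approach turns out not to matter, almost nothing is lost.

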Specific aims: Does the use of perioperative pharmacologic agents (subcutaneous heparin; 5,000 units given before surgery and every 8 hours after surgery until discharge), compared to IPCs alone, for RP for prostate cancer:

1. Prevent the occurrence of symptomatic VTE following surgery? (primary efficacy outcome)
2. Increase the incidence of clinically significant lymphocele? (primary safety outcome)
3. Increase the incidence of clinically significant hematoma? (primary safety outcome)
4. Increase the incidence of major bleeding following surgery? (primary safety outcome)
5. Prevent the occurrence of any VTE (asymptomatic or symptomatic) following surgery? (secondary outcome)
6. Increase estimated blood loss during surgery? (secondary outcome)
7. Increase surgical drain output after surgery? (secondary outcome)

8. Lead to potential surveillance bias measured by increased or decreased use of diagnostic imaging for VTE relative to symptoms (e.g. lower extremity Duplex ultrasound, spiral CT angiography, V/Q scan, etc.)? (secondary outcome)

3. Background (briefly describe pre-clinical and clinical data, current experience with procedures, drug or device, and any other relevant information to justify the research)

An estimated 180,000 new cases of prostate cancer were diagnosed in 2016, and about 90,000 radical prostatectomies are performed in the United States annually [1-3]. Since the year 2000, a sharp change in practice patterns has shifted the traditionally open radical prostatectomy (RP) procedure to current practice where the great majority (likely >70%) are robotic-assisted laparoscopic RPs (RALRP) [3]. According to most guidelines, undergoing RP by any approach classifies a patient as high-risk for venous thromboembolism (VTE), including deep venous thrombosis (DVT) and pulmonary embolism (PE), and would lead to implementation of appropriate intermittent mechanical pneumatic compression devices (IPCs) and pharmacologic prophylaxis [4-8].

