Patients randomized to the pharmacologic VTE prophylaxis arm will receive a dose of subcutaneous heparin 5,000 units within 2 hours prior to incision, and subcutaneous heparin 5,000 units every 8 hours after surgery until discharge. Total number of doses received and missed doses will be recorded. No post-discharge pharmacologic prophylaxis will be prescribed. Per routine care, patients will be requested to inform their urologist's office if they experience any symptoms of DVT or PE, or any other concerns, during the first 30 days after surgery. All patients will receive a phone call around 30 days after surgery to assess primary outcomes including documentation of whether they experienced a postoperative VTE episode and any treatment initiated for confirmed VTE. Any patient endorsing symptoms concerning for VTE up to 30 days after surgery will be recommended to undergo urgent evaluation and care, locally or at Johns Hopkins, with imaging/evaluation results forwarded to Johns Hopkins. Patients and their insurance will be responsible for the costs as part of routine care. The 30-day phone call will be the only planned, study-initiated contact after surgery with the patient to evaluate symptomatic outcomes and will be the same for both the control and pharmacologic prophylaxis arms.

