Urologists will initially be blinded to patient randomization and the administration of the preoperative subcutaneous heparin dose to prevent bias on recorded estimated blood loss during the surgery. Postoperatively, administration of subcutaneous heparin will be unblinded during the patient's inpatient stay. Control patients will receive IPCs only and no placebo doses will be administered during their hospital stay. Data analysis will be blinded as to treatment group. Performance and interpretation of lower extremity Duplex screening ultrasound will be blinded to patient randomization. Surveillance bias will be assessed by differential performance of postoperative imaging as described above.

- d. Justification of why participants will not receive routine care or will have current therapy stopped.

All patients will receive routine care. Both arms include patients receiving accepted standards of care.

- e. Justification for inclusion of a placebo or non-treatment group.

The control group in this trial is the group receiving current routine practice at Johns Hopkins with IPCs. The experimental group is the group receiving pharmacologic VTE prophylaxis as practiced at other centers and recommended by most VTE guidelines for major surgery.

- f. Definition of treatment failure or participant removal criteria.

Participants will be removed from the trial if surgery is canceled or not completed for any reason. All patients assigned to the experimental and control arms completing surgery will be included in the study regardless of compliance with pharmacologic prophylaxis doses in an intention-to-treat (ITT) analysis. Patients experiencing an adverse event will be provided appropriate care. Additional per-protocol analyses will be conducted to compare outcomes by compliance with assigned regimen. Patients diagnosed with VTE events will be recommended to obtain routine care locally or at Johns Hopkins per patient preference.

- g. Description of what happens to participants receiving therapy when study ends or if a participant's participation in the study ends prematurely.

Perioperative pharmacologic prophylaxis is only given during the patient's inpatient stay. As mentioned above, all patients will be included in an ITT analysis as possible if they undergo surgery. No planned outcomes will be tracked after the 30-day post-surgical outcomes unless the patient initiates contact.

5. Inclusion/Exclusion Criteria

Inclusion:

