The secondary outcomes (all regarded separately) will be estimated blood loss from surgery, total surgical drain output after surgery (for patients with surgical drains), the overall incidence of VTE (asymptomatic or symptomatic) determined from the subcohort undergoing lower extremity Duplex screening ultrasound, and surveillance bias (measured by use of postoperative diagnostic imaging). Estimated blood loss will be recorded from the anesthesia data report from surgery. Total surgical drain output will be recorded based on ins and outs flowsheets routinely recorded by nurses when emptying drains. Surveillance bias will be determined by recording the type and frequency of postoperative imaging performed while a patient is in the hospital or within 30 days of surgery after discharge.

The overall rate of VTE will only be determined for patients in the subcohort. The asymptomatic VTE will be determined based on the results of the screening lower extremity Duplex ultrasound for asymptomatic DVTs. The overall rate of VTE will be determined by adding the number of asymptomatic VTE events to the number of symptomatic VTE events experienced in the subcohort.

d. Statistical plan including sample size justification and interim data analyses.

Pharmacologic VTE prophylaxis can be expected to prevent between 67% to 75% of DVTs [33]. Given the lowest expected primary outcome event rate will be for VTE, the trial sample size will be based on a power of 80% ($\beta=0.2$) and one-sided α of 0.05 for prevention of post-operative VTE with pharmacologic prophylaxis reducing the rate from 5% to 1.5%. Including two interim analyses of the primary endpoint as outlined in the Interim Analyses section below, the total sample size needed will be 666 (333 per treatment arm) based on 2000 simulations for 82% power (exact α -spending and futility boundaries are outlined below). As mentioned above, the primary efficacy analysis will compare symptomatic VTE rates at the 30-day follow-up for all patients. Secondary analyses will be conducted to compare secondary outcomes between treatment arms at the completion of the study as well. It is expected that during full-time patient enrollment, the study would require about 2 years to accrue patients assuming 50% enrollment.

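### Drain output is compared only in patients who received a drain, after the first heparin dose; the plan's caveat is too narrow, its ITT sentence makes no exception, and drain placement is not compared by arm

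*Combined protocol and SAP*

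**What the plan says.** Section 2 lists aim 7 as "Increase surgical drain output after surgery? (secondary outcome"). Sections 4a and 7c define the outcome as "total surgical drain output after surgery (for patients with surgical drains"). In section 7d (Statistical analyses) it is compared by t-test or Wilcoxon test, with linear regression for adjusted analyses.

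Section 7d then gives a caveat: "Note that analysis of drain output is confined to patients with drains placed, so it is not protected by the randomization". The same sentence goes on to describe this feature as "potentially limiting interpretability if the number of patients is small and confounding factors are not well balanced". The sentence after that reads "All analyses of primary and secondary outcomes will be based on intention to treat (ITT"), with no exception for drain output. Section 4f describes the ITT population: "All patients assigned to the experimental and control arms completing surgery will be included in the study regardless of compliance" (that is, however many heparin doses were given).

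On timing, section 4a states that patients in the heparin arm "will receive a dose of subcutaneous heparin 5,000 units within 2 hours prior to incision". Section 6a gives a 3-hour window instead. The two need reconciling, but under either the dose comes before any surgical drain. On blinding, section 4c states: "Urologists will initially be blinded to patient randomization and the administration of the preoperative subcutaneous heparin dose". Treatment is open after surgery.

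The documents do not state what share of patients get a drain, who decides, when, or on what grounds. They plan no comparison of drain placement between arms.

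**The concern.** Having a drain is a post-randomisation event. If heparin makes the operative field wetter, and a wetter field makes a drain more likely, the heparin arm's drained group gains patients who would otherwise have gone without one. On average these have less to drain than patients who would have been drained anyway, so the heparin mean falls relative to control. The comparison could then understate the increase that aim 7 looks for.

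The plan's caveat describes chance imbalance, which shrinks as numbers grow. Selection caused by treatment does not: a larger sample only estimates the biased quantity more precisely. The planned regression is not a dependable remedy. Section 7d's list of factors to check for imbalance includes operative time and blood loss. Both are measured after the first dose and blood loss is itself a secondary outcome, so adjusting for them could remove part of the effect being sought.

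Two reporting consequences follow. A reader who takes the ITT sentence at face value would treat the drain result as a randomised comparison. And a higher share drained under heparin, which would itself bear on aim 7, would not be reported.

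**Working it through.** The plan gives no effect size, SD, drain rate or power for drain output, so there is no stated figure to reproduce. The 666 patients (333 per arm) are sized for symptomatic VTE.

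**Assumed inputs (none from the documents).**
- Bleeding index L is standard normal in controls; heparin shifts it by d = 0.30 SD. It stands for what drives drain output.
- A drain is placed when a propensity u, standard normal in controls with correlation ρ to L, exceeds a cut c. With 50% of controls drained, c = 0.
- A share k of heparin's effect is already present at placement, so u shifts by ρkd.

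The share k matters because only one dose precedes incision, while section 11 expects 4 to 7 doses in all. Postoperative doses can add to output but cannot affect placement of a drain at surgery. k = 1 is the extreme case; k = 1/4 corresponds to one dose of four, if effect were proportional to dose.

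**Formula.** With λ(x) = φ(x)/(1 − Φ(x)), the mean of L among drained controls is ρλ(c), and among drained heparin patients it is d + ρλ(c − ρkd). So

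drained-only difference = d − ρ[λ(c) − λ(c − ρkd)].

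**Example, ρ = 0.7, k = 1.** ρkd = 0.21; λ(0) = 0.798 and λ(−0.21) = 0.669. The loss is 0.7 × 0.129 = 0.090, so the difference is 0.210 instead of 0.300, a 30% understatement. The share drained under heparin is Φ(0.21) = 58%.

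**Understatement (%) with 50% of controls drained:**

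| ρ | k = 1 | k = 1/2 | k = 1/4 | heparin share drained, k = 1 | same, k = 1/4 |
|---|---|---|---|---|---|
| 0 | 0 | 0 | 0 | 50.0% | 50.0% |
| 0.3 | 5.6 | 2.8 | 1.4 | 53.6% | 50.9% |
| 0.5 | 15.5 | 7.9 | 4.0 | 56.0% | 51.5% |
| 0.7 | 30.0 | 15.3 | 7.7 | 58.3% | 52.1% |
| 0.9 | 49.1 | 25.2 | 12.7 | 60.6% | 52.7% |

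**Other control drain rates, ρ from 0.3 to 0.9:**

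| Controls drained | k = 1 | k = 1/4 |
|---|---|---|
| 30% | 6.6–57.7% | 1.7–14.8% |
| 70% | 4.5–38.0% | 1.1–10.1% |
| 90% | 2.5–20.3% | 0.6–5.6% |

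Sample size does not appear in the formula, which is why the small-numbers condition does not cover this problem.

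**A variant.** Suppose heparin raises placement (by 0.3ρ on the propensity scale) but leaves output unchanged, and output correlates 0.7 with bleeding. The drained-only difference then runs from −0.01 to −0.12 SD over control drain rates of 30–90% and ρ of 0.3–0.9, so heparin would appear to lower output.

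**The case against.** The plan's authors have a fair reply. They disclose the restriction and say outright that it costs the protection of randomisation, so a reader who inferred that the problem is concealed would be wrong. The text says interpretability is potentially limited if numbers are small; it does not say only if. That stands: the fault is a caveat that is too narrow and has no remedy attached.

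A reader might also infer that drains are chosen in the operating room in response to bleeding. The documents do not support this. Physical placement must follow the pre-incision dose, but the decision could rest on habit or on a planned lymphadenectomy, and then there is no bias. Near-universal drain use would also keep it small. The surgeon is blinded to arm during the operation, which rules out conscious influence of the assignment, though not influence through visible bleeding.

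The ITT conflict is modest. The restriction stands in the sentence just before, and ITT can be read as analysis by assigned arm regardless of compliance. One exempting clause settles it.

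Finally, a reader might infer that the trial's safety conclusions are compromised. They are not: major bleeding, hematoma and lymphocele are primary safety outcomes assessed in all patients and reviewed at interim analyses, and blood loss is a separate secondary outcome not confined to drained patients.

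**Conclusion.** The point holds as a minor one about a single secondary outcome. From the text alone: the comparison is restricted by an event after the first dose, the caveat ties the limitation to conditions that do not govern treatment-related selection, the ITT sentence makes no exception, and placement is not compared by arm.

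Whether the result is actually biased is conditional on intraoperative bleeding influencing placement, which the documents neither state nor exclude. At 50% of controls drained and an assumed 0.30 SD effect, the understatement is 0% if the two are unrelated. For correlations of 0.3 to 0.9 it is 6–49% with the whole effect present at placement, 3–25% with half and 1–13% with a quarter. The downward direction belongs to the assumed model. The stronger conclusion, that a real heparin effect on drainage will be understated, does not follow from the documents.

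**What to change.** 1. Add a planned ITT analysis, reported beside drain output: the proportion with a drain placed, by assigned arm, in all patients completing surgery, with a confidence interval.
2. Exempt drain output from the ITT sentence, label it a drained-subset, non-randomised comparison, and delete the condition about small numbers.
3. Limit covariates in its adjusted analysis to factors fixed before randomisation, which excludes blood loss and operative time.

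A blinded pre-incision record of whether a drain is intended, with a comparison in the planned-drain group, could be added as a sensitivity analysis. It should not replace the main analysis: it drops unplanned drains, its size is unknown, and scoring a planned but unplaced drain as zero would mix placement with output.

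The cost is one extra tabulation and a more cautious claim for one secondary outcome. The tabulation also has limits. With 333 per arm and about 50% drained, the 95% half-width for the difference is 1.96 × √(2 × 0.5 × 0.5/333) = 7.6 percentage points. It would tend to show shifts near the 11 points at the top of the table but not those of 1 to 3 points, so a null placement result should not be read as proof that selection is absent.
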